3.3.4 Exploratory Objective 4 and Endpoints

The exploratory objective 4 of this study is to describe reinforcing effects related to tobacco/nicotine containing products use in smokers switching from CIG smoking to P4M3 (CA35 and CM35 arms combined and separately) compared to continued CIG smoking.

Endpoints (Day -1 to Day 5)

- Subscale scores of Product Experience (ABOUT - Product Experience) (assessed only in subjects randomized to P4M3 or CIG)

3.3.5 Exploratory Objective 5 and Endpoints

The exploratory objective 5 of this study is to describe the Human Puffing Topography (HPT) over the entire exposure period in subjects switching to P4M3 (CA35 or CM35 arms combined and separately).

Endpoints (Day 1 to Day 5)

- Puffing topography parameters as per-product use experience and per-day parameters ([Appendix C](#)).

3.3.6 Exploratory Objective 6 and Endpoints

The exploratory objective 6 of this study is to evaluate the cytochrome P450 1A2 (CYP1A2) enzymatic activity in smokers switching to P4M3 (CA35 and CM35 arms combined and separately) and smoking abstinence compared to continued CIG smoking.

Endpoint (Day -1, Day 5)

- Molar metabolic ratio of paraxanthine/caffeine in plasma.

Confidentiality Statement

[figure not shown]
Data and information contained in this document are considered to constitute trade secrets and confidential commercial information, and the legal protections provided to such trade secrets and confidential information are hereby claimed under the provisions of applicable law. No part of this document may be publicly disclosed without the written consent of Philip Morris Products S.A

4 Investigational Plan

4.1 Overall Study Design and Plan

This is a randomized, controlled, open-label, 4-arm parallel study with a stratified randomization by sex. Quotas will be applied to ensure that the randomized subjects contain at least 40% of both sexes (males and females) per arm.

This is an *ad libitum* smoking/vaping study with unrestricted product use (P4M3 or CIG, in the respective arms) for 5 days exposure period in confinement followed by a 3-day Safety follow-up period (Figure 2).

Abbreviations:

CA35 = P4M3 Classic Auburn 3.5% nicotine; CM35 = P4M3 Classic Menthol 3.5% nicotine; CIG = Cigarette; SA = Smoking abstinence

Figure 2 Study Design

- Screening period (from Day -30 until Day -3):

The screening period covers up to four weeks prior to admission. A presentation of P4M3 (without product use) will be done by the site staff during the Screening visit. All subjects will receive information on the risks of smoking and smoking cessation advice. Eligible subjects will return to the investigational site for verification of eligibility.

Confidentiality Statement

Data and information contained in this document are considered to constitute trade secrets and confidential commercial information, and the legal protections provided to such trade secrets and confidential information are hereby claimed under the provisions of applicable law. No part of this document may be publicly disclosed without the written consent of Philip Morris Products S.A.

- Admission (from Day -2 until morning of Day -1):

On Day -2 (admission), after all inclusion/exclusion criteria are checked, all eligible subjects will be enrolled and perform a product test using both P4M3 variants: tobacco flavor “Classic Auburn” 3.5% nicotine (CA35) and menthol flavor “Classic Menthol” 3.5% nicotine (CM35), with an *ad libitum* use regimen for a duration of approximately 10 minutes *ad libitum* use per flavor. After the product test, subjects not willing to use P4M3 during the study will be discontinued and will be replaced. Subjects willing to continue participation will start their confinement period. CIG smoking will be allowed *ad libitum* from the time of admission of the subject until approximately 11:00 PM, except before/during assessments requiring smoking breaks. Use of any TNP other than CIG (and P4M3 for the product test) will not be allowed after admission.

Provided that the 28-day Screening period is not exceeded, alternate subjects (not yet randomized) have to repeat the Admission visit of the following group to re-confirm their eligibility for randomization.

- Baseline (from Day -1, 06:30 AM until Day 1, 06:29 AM):

Subjects may continue smoking their CIG *ad libitum*, except before/during assessments requiring smoking breaks. The 24-hour urine collection for Day -1 will start in the morning of Day -1 (urine collection details provided in [Appendix A](#)). Baseline assessments will be performed as indicated in [Appendix A](#).

On Day -1, subjects will be randomized. Subjects will be informed about their randomized study arm by the study site staff on Day 1 prior to start of product use. The four randomization arms are:

- P4M3 CA35 arm: 18 subjects, *ad libitum* use of P4M3 using CA Cartridges
- P4M3 CM35 arm: 18 subjects, *ad libitum* use of P4M3 using CM Cartridges
- CIG arm: 18 subjects, *ad libitum* use of their own preferred CIG brand
- SA arm: 18 subjects who will abstain from CIG smoking

- Exposure period in confinement setting (from Day 1 until Day 5 11:00 PM, followed by Discharge at Day 6):

The exposure period in confinement consists of 5 days of *ad libitum* use of the assigned product in the P4M3 and CIG arms. Use of any TNP other than the assigned product will not be allowed and may, at the discretion of the investigator, result in the subject’s discontinuation from the study. Subjects allocated to the SA arm will be asked to abstain from CIG smoking.

Confidentiality Statement

Data and information contained in this document are considered to constitute trade secrets and confidential commercial information, and the legal protections provided to such trade secrets and confidential information are hereby claimed under the provisions of applicable law. No part of this document may be publicly disclosed without the written consent of Philip Morris Products S.A

Daily 24-hour urine will be collected from Day 1 to Day 5. On Day 1, product use must not start before the end of 24-hour urine collection of Day -1. The 24-hour urine collection period for Day 5 will end in the morning of Day 6 prior to Discharge.

During the confinement period, site staff will distribute assigned products to the subjects and record all products distributed in the source documentation.

Any subject who wants to attempt to quit using tobacco or nicotine containing products at any time during the study (i.e., P4M3, CIG) will be encouraged to do so and will be referred to appropriate medical services. This will not affect subject's financial compensation, and the subject will remain in the study.

- Safety follow-up period (from Discharge at Day 6 until the end of the Safety follow-up period):

After Discharge at Day 6 or from the day of early termination, subjects will enter a 3-day safety follow-up period during which AE/SAEs reported by the subjects will be collected and the follow-up of AEs/SAEs ongoing at Discharge will be conducted by the investigational site.

4.2 Rationale for Study Design

This clinical study aims to demonstrate the reduction of BoExp to selected HPHC in smokers switching from CIG to P4M3, a candidate RRP¹, as compared smokers continuing smoking CIG, or to smoking abstinence (SA). A reduction of exposure to HPHC derived from CIG smoke is expected to diminish the health risk of nicotine consumption if switching completely to ENDS.

The exposure period in confinement will provide information on exposure reductions achievable in a well-controlled environment with full control on daily P4M3/CIG consumption and compared to SA.

HPHC considered to be of health concern have been reported by different regulatory bodies and health organizations [12, 13]. Lists of HPHC to be reported in tobacco smoke have consequently been developed, as described, for example in the FDA draft guidance on "Reporting Harmful and Potentially Harmful Constituents in Tobacco Products and Tobacco Smoke" [14]. More recently, a guidance was issued by the FDA on which HPHC to be considered for reporting in e-liquids or aerosols of ENDS [15].

¹ Reduced risk products ("RRPs") is the term used by PMI to refer to products that present, are likely to present, or have the potential to present less risk of harm to smokers who switch to these products versus continued smoking.

Confidentiality Statement

Data and information contained in this document are considered to constitute trade secrets and confidential commercial information, and the legal protections provided to such trade secrets and confidential information are hereby claimed under the provisions of applicable law. No part of this document may be publicly disclosed without the written consent of Philip Morris Products S.A

It is not possible to measure each of those potentially toxic constituents in humans, due to constraints in availability of validated, reliable methods, or simply the absence of suitable BoExp. A selection of HPHC to be evaluated in this study was thus performed based on the following criteria:

1. The HPHC selected are representative of a variety of chemical classes and organ toxicity classes as defined by the FDA (carcinogen, cardiovascular toxicant, respiratory toxicant, reproductive and development toxicant, and addiction potential) [13]
2. The HPHC reflects a specific toxic exposure or is a reliable surrogate of exposure to HPHC
3. The HPHC assessed cover a broad range of formation temperatures
4. The HPHC is specific to smoking with other sources being minor or non-existent
5. The BoExp to a HPHC is reliably detectable using validated, reproducible, precise analytical methods
6. The BoExp to a HPHC has a half-life that is suitable with the schedule of assessments

Other parameters such as product evaluation, and subjective effects related to smoking including smoking urges and withdrawal symptoms, and the intent to use, will be evaluated.

Twenty-four hours urine collection conducted in this study is the standard method to measure the levels of excretion of BoExp.

All subjects in the CIG arm will be asked to buy their own CIG according to their anticipated needs for the study to minimize any changes in their smoking behavior.

4.3 Appropriateness of Measurements

All laboratory measures utilized for this study are validated and are appropriate for the study assessments.

All the self-report measures to be used in this study have been developed following the best practices (including the FDA's Guidance for Industry Patient-Reported Outcome (PRO) Measures [16]), which provide the scientific basis for the development, modification, and validation of PRO measures in support of clinical and regulatory research. They are validated and previously published or adapted versions of validated questionnaires.

4.4 Study Duration

The entire study duration per subject will be 11 to 38 days. This will include a screening period of up to 28 days prior to Admission (Day -30 to Day -3), followed by a 7-day

Confidentiality Statement

Data and information contained in this document are considered to constitute trade secrets and confidential commercial information, and the legal protections provided to such trade secrets and confidential information are hereby claimed under the provisions of applicable law. No part of this document may be publicly disclosed without the written consent of Philip Morris Products S.A.

confinement period (Day -2 to Day 5, and Discharge on Day 6), and a 3-day Safety follow-up period.

The EOS for a randomized subject is defined as the completion of the 3-day Safety follow-up period either after Discharge on Day 6, or after the date of early termination of the subject. The EOS of the entire study is the end of the Safety Follow-up Period for the last subject.

Confidentiality Statement

Data and information contained in this document are considered to constitute trade secrets and confidential commercial information, and the legal protections provided to such trade secrets and confidential information are hereby claimed under the provisions of applicable law. No part of this document may be publicly disclosed without the written consent of Philip Morris Products S.A

5 Study Population

Approximately 72 smoking healthy female or male subjects who have smoked on average at least 10 regular or menthol CIG per day for the last 4 weeks prior to Admission will be randomized (stratified by sex) into this study. Quotas will be applied to ensure that the randomized subjects contain at least 40% of both sexes (males and females) per arm.

The maximum number of CIG smoked daily is not limited. Subjects must have been smoking for at least 3 years of smoking prior to the Screening Visit. There will be no brand restrictions of CIG. Smoking status will be verified with a urinary cotinine test (cotinine ≥ 200 ng/mL).

5.1 Selection of Study Population

5.1.1 Inclusion Criteria

Subjects who meet all the following inclusion criteria can be enrolled into the study:

Inclusion Criteria	Screening	Day -2
1. Subject has signed the ICF and is able to understand the information provided in the ICF.	X	
2. Subject is male or female and between 21 and 65 years old (inclusive).	X	
3. Subject has been a smoker for ≥ 3 years prior to the screening visit (smoking cessation attempts during this period, if any, did not last >6 months).	X	
4. Subject has continuously smoked on average ≥ 10 commercially available mentholated or non-mentholated CIGs per day over the last 4 weeks prior to screening and admission. Smoking status will be verified based on a urinary cotinine test (cotinine ≥ 200 ng/mL).	X	X
5. Subject is healthy as judged by the Investigator based on available assessments from the screening period (e.g., safety laboratory, spirometry, vital signs, physical examination, ECG, and medical history).	X	

Confidentiality Statement

Data and information contained in this document are considered to constitute trade secrets and confidential commercial information, and the legal protections provided to such trade secrets and confidential information are hereby claimed under the provisions of applicable law. No part of this document may be publicly disclosed without the written consent of Philip Morris Products S.A

5.1.2 Exclusion Criteria

Subjects who meet any of the following exclusion criteria must not be enrolled into the study:

Exclusion Criteria	Screening	Day -2
1. As per the Investigator's judgment, the subject cannot participate in the study for any reason other than medical (e.g., psychological, social reason).	X	
2. Subject is legally incompetent, or physically or mentally incapable of giving consent (e.g., in emergency situations, under guardianship, or prisoners).	X	
3. Subject has a clinically relevant disease which requires medication (including but not limited to gastrointestinal, renal, hepatic, neurological, hematological, endocrine, oncological, urological, immunological, pulmonary, and cardiovascular disease) or any other medical condition (including safety laboratory), which as per the judgment of the Investigator would jeopardize the safety of the subject.	X	
4. Subject experienced within 30 days prior to screening/admission a body temperature >37.5°C or an acute illness (e.g., upper respiratory-tract infection, viral infection, etc.)	X	X
5. As per the Investigator's judgment, the subject has medical conditions which do or will require a medical intervention (e.g., start of treatment, surgery, hospitalization) during the study participation, which may interfere with the study participation and/or study results.	X	
6. Subject has relevant history of, or current asthma condition or COPD condition, and/or clinically significant spirometry findings at Screening or Baseline	X	
7. Subject has donated blood or received whole blood or blood products within 3 months prior to screening.	X	
8. BMI <18.5 kg/m ² or ≥32.0 kg/m ² .	X	
9. Positive serology test for HIV 1/2, HBV, or HCV.	X	

Confidentiality Statement

Data and information contained in this document are considered to constitute trade secrets and confidential commercial information, and the legal protections provided to such trade secrets and confidential information are hereby claimed under the provisions of applicable law. No part of this document may be publicly disclosed without the written consent of Philip Morris Products S.A

10. Subject has a positive alcohol breath test and/or has a history of alcohol abuse which as per judgement of the PI could interfere with their participation in the study.	X	X
11. The subject has a positive urine drug test.	X	X
12. Subject or one of their family members ^a is a current or former employee of the tobacco or e-cigarette industry.	X	
13. Subject or one of their family members ^a is employee of the investigational site or of any other parties involved in the study.	X	
14. Subject has participated in another clinical study within 1 month or five half-lives of the previous investigational drug/product (whichever the longer) prior to Screening.	X	
15. Subject has been previously screened or enrolled in this study.	X	
16. Subject is pregnant (does not have negative pregnancy tests at screening and at admission) or is breastfeeding.	X	X
17. For women of childbearing potential only ^b : subject does not agree to use an acceptable method of effective contraception. ^c	X	

a. *As defined by FDA guidance on Human Subject Protection (21 CFR 50.3(l), (m), 50.24(a)(6), (a)(7)(v), b): "Family member" means among other things "parent", "spouse", "brothers, sisters, and spouses of brothers and sisters" and "any individual related by affinity...whose close association with the subject is equivalent of a family relationship"*

b. *Women who are not of childbearing potential meet at least one of the following criteria:*

- *Have undergone hysterectomy, bilateral oophorectomy, or bilateral tubal ligation,*
- *Have primary ovarian insufficiency, or*
- *Are medically confirmed to be post-menopausal (cessation of regular menses for at least 12 consecutive months with no alternative pathological or physiological cause).*

c. *Intrauterine device, intrauterine system, barrier methods of contraception (condoms, occlusive caps) with spermicidal foam/gel/film/suppository, hormonal contraception, vasectomized partner(s), or true abstinence (periodic abstinence and withdrawal are not effective methods) from Screening until the end of the Safety Follow-Up Period.*

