Data and information contained in this document are considered to constitute trade secrets and confidential commercial information, and the legal protections provided to such trade secrets and confidential information are hereby claimed under the provisions of applicable law. No part of this document may be publicly disclosed without the written consent of Philip Morris Products S.A.

Abbreviations:

CA35 = P4M3 Classic Auburn 3.5% nicotine; CM35 = P4M3 Classic Menthol 3.5% nicotine; CIG = Cigarette; SA = Smoking abstinence

Figure 1 Study Design

- Screening period (from Day -30 until Day -3):

The screening period covers up to four weeks prior to admission. A presentation of P4M3 (without product use) will be done by the site staff during the Screening visit. All subjects will receive information on the risks of smoking and smoking cessation advice. Eligible subjects will return to the investigational site for verification of eligibility at Admission visit.

- Admission (from admission on Day -2 until morning of Day -1):

On Day -2 (Admission), after all selected inclusion/exclusion criteria have been verified, all eligible subjects will be enrolled and perform a product test using both P4M3 variants: tobacco flavor “Classic Auburn” 3.5% nicotine (CA35) and menthol flavor “Classic Menthol” 3.5% nicotine (CM35) for a duration of approximately 10 minutes *ad libitum* use per flavor. After the product test, subjects not willing to use P4M3 during the study will be discontinued and will be replaced. Subjects willing to continue participation will start their confinement period. CIG smoking will be allowed *ad libitum* from the time of admission of the subject until approximately 11:00 PM, except before/during assessments requiring smoking breaks. Use of any tobacco/nicotine containing product

Confidentiality Statement

Data and information contained in this document are considered to constitute trade secrets and confidential commercial information, and the legal protections provided to such trade secrets and confidential information are hereby claimed under the provisions of applicable law. No part of this document may be publicly disclosed without the written consent of Philip Morris Products S.A.

(TNP) other than CIG (and P4M3 for the product test) will not be allowed after admission.

- Baseline (from Day -1, 06:30 AM until Day 1, 06:29 AM):

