7.4.4 Body Height and Weight

Body weight and height will be recorded at the Screening Visit, body weight will also be recorded at Admission Visit Day -2.

The BMI will be calculated from the body weight and height using the following formula:

$$\text{BMI} = \frac{\text{weight in kilograms}}{\text{height in meters}^2} = \frac{kg}{m^2}$$

The BMI will be used to assess eligibility for enrolment.

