#### Confidentiality Statement

Data and information contained in this document are considered to constitute trade secrets and confidential commercial information, and the legal protections provided to such trade secrets and confidential information are hereby claimed under the provisions of applicable law. No part of this document may be publicly disclosed without the written consent of Philip Morris Products S.A

Sex	Female Male	Stratification factor used for randomization and statistical analysis
Race	American Indian OR Alaska Native Asian Black Native Hawaiian OR Other Pacific Islander White	Stratification factor used for statistical analysis
BMI (kg/m  )	Normal $\geq 18.5$ and $< 25.0$ Overweight $\geq 25.0$ and $< 30.0$ Obese $\geq 30.0$ and $< 32.0$	Derived
	Note that patients with BMI $< 18.5$ (underweight) and $\geq 32$ (Obese) are excluded from the study as per the inclusion/exclusion criteria.	
FTND total score	Mild: 0-3 Moderate: 4-6 Severe: 7-10	Derived

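### The blood-donation and other-study exclusions look back from screening only, leaving up to 28 days before enrolment uncovered, and the protocol gives conflicting rules for the Day -2 eligibility check

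*Protocol*

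**What the plan says.** **The two windows.** Protocol section 5.1.2, exclusion 7: "Subject has donated blood or received whole blood or blood products within 3 months prior to screening". Exclusion 14: "Subject has participated in another clinical study within 1 month or five half-lives of the previous investigational drug/product", whichever is longer, again counted back from screening. Both carry a tick in the Screening column and none in the Day -2 column. SAP section 4.5.2 repeats them.

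**Criteria that do reach admission.** Inclusion 4 covers smoking "over the last 4 weeks prior to screening and admission". Exclusion 4 (fever or acute illness) and exclusion 16 (pregnancy) also name admission. All three are ticked at both visits.

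**The Day -2 check.** The synopsis enrols subjects "after all selected inclusion/exclusion criteria have been verified". Section 4.1 enrols them "after all inclusion/exclusion criteria are checked", and SAP section 4.1 follows it. Section 9.2.1 makes Day -2 enrolment conditional on every criterion being satisfied. Footnote d of Appendix A says the criteria are re-checked and names no subset. The criteria tables tick only inclusion 4 and exclusions 4, 10, 11 and 16 at Day -2.

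**BMI.** Exclusion 8 is ticked at Screening only. Weight is taken again on Day -2, Table 10 lists a BMI calculation before enrolment, and section 7.4.4 states: "The BMI will be used to assess eligibility for enrolment". SAP Table 7 assumes that subjects outside the limits "are excluded from the study as per the inclusion/exclusion criteria", and SAP section 9.3 summarises BMI at admission as well as at screening.

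**The concern.** An entry criterion with a look-back window should normally be measured from the point at which the subject enters the trial. Here that point is Day -2: subjects are enrolled, use both P4M3 variants the same day, and start confinement. For exclusions 7 and 14 the window closes earlier, at screening, and nothing in the criteria covers the time between.

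The stakes are subject safety and a clean baseline. A donation or transfusion just before confinement, or exposure to another investigational product, is what these two exclusions are there to keep out.

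The conflicting descriptions of the Day -2 check have a further consequence in the analysis. SAP Table 12 treats any violation of the inclusion or exclusion criteria as a major deviation, and the blinded data review team decides whether it affects evaluability. That decision governs membership of the per-protocol set, on which the primary analysis is run, with 18 subjects randomized per arm. Whether an out-of-range Day -2 BMI counts as a violation should be settled in the protocol and not left to that review.

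**Working it through.** The check is a count and a calendar comparison; no power or sample-size formula applies.

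**Calendar.** The plan's own figures reproduce, with no Day 0:
- Screening, Day -30 to Day -3: 28 days. Confinement, Day -2 to Day 5: 7 days. Follow-up: 3 days.
- Maximum 28 + 7 + 3 = 38 days; minimum 1 + 7 + 3 = 11 days. This matches the 11 to 38 days in section 4.4.
- Longest gap from screening to Day -2: -2 - (-30) = 28 days. Shortest: -2 - (-3) = 1 day.
- Section 9.1.1 allows 28 days before enrolment, while section 9.2.1 says 27 days. These two also need to be reconciled.

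**Ticks.** There are 5 inclusion and 17 exclusion criteria, 22 in all. Day -2 ticks: 1 inclusion (no. 4) + 4 exclusions (nos. 4, 10, 11, 16) = 5.

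**What the windows cover.** Take 3 months as about 90 days and 1 month as about 30 days (an assumption, for illustration), with screening on Day -30:

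| Event | Days before Day -2 | Excluded as worded? |
|---|---|---|
| Blood donation 90 days before screening | 90 + 28 = 118 | Yes |
| Blood donation on Day -29 | 27 | No |
| Blood donation on Day -3 | 1 | No |
| Other study ending 30 days before screening | 30 + 28 = 58 | Yes |
| Other study entered and left between screening and Day -2 | 1 to 27 | No |

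The older event excludes and the more recent one does not. Re-checking all 22 criteria on Day -2 changes nothing, because on that day the text of exclusions 7 and 14 still asks about the period before screening.

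**BMI.** The upper limit is 32.0 kg/m². At an assumed height of 1.70 m, 31.7 × 1.70² = 91.6 kg and 32.0 × 1.70² = 92.5 kg. A gain of 92.5 - 91.6 = 0.9 kg between the visits gives a Day -2 value that sections 7.4.4 and 9.2.1 treat as relevant to enrolment and that the exclusion 8 tick places outside the Day -2 check. This is a deliberately borderline case; the documents give no basis for saying how often it would occur.

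**The case against.** The strongest reply is that the body of the protocol already governs Day -2. Section 5.1.2 opens with "Subjects who meet any of the following exclusion criteria must not be enrolled into the study", section 9.2.1 requires all criteria to be met, and Table 10 lists the criteria check without a subset. The ticks need not be exhaustive: exclusion 6 is ticked at Screening only yet names findings at Baseline. For criteria with no time anchor this reply is sound. It does not reach exclusions 7 and 14, whose own wording stops at screening.

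Several stronger readings are tempting and are not supported:

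- **That 17 criteria go unprotected.** Many of the unticked items are fixed, or tied to screening by definition: signed consent, age, years of smoking before screening, having been screened before.
- **That the Day -2 BMI has no rule.** It has one, in section 7.4.4, Table 10 and section 9.2.1. The defect is that the exclusion 8 tick conflicts with it.
- **That a subject who becomes ineligible would still be enrolled.** For unanchored criteria this follows only if the ticks or the synopsis override sections 4.1 and 9.2.1. For exclusions 7 and 14 the subject never becomes ineligible as worded.
- **That alternates have only five items re-confirmed.** They repeat the whole Admission visit.
- **That the P4M3 pharmacokinetic study in section 2.1.2 would feed subjects into this one.** The protocol says only that it has been submitted, with no site or dates.

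It is also fair to say that the approximately 81 mL blood volume is this study's own total, compared with a standard donation; the protocol makes no claim about cumulative loss.

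There are backstops. Hematology is repeated on Day -1, section 5.2 allows discontinuation for a condition of concern, and section 5.4 handles violations case by case. They are partial: they act after the Day -2 product test, and section 5.4 cannot be triggered by an event that violates nothing.

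**Conclusion.** The point holds for exclusions 7 and 14. As worded they leave between 1 and 28 days before enrolment uncovered (at most 27 if section 9.2.1 governs), and no reading of the Day -2 check closes the gap. It does not look deliberate, since inclusion 4 and exclusions 4 and 16 all name admission, but the documents give no rationale either way.

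The second part is an inconsistency. The synopsis, sections 4.1 and 9.2.1, Appendix A and the criteria tables do not agree on what is checked on Day -2, and BMI is the clearest case. The documents do not show that an ineligible subject would in fact be enrolled through it; they show that a site could not tell which text to follow.

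The effect is on who can be enrolled and exposed and, through the deviation review, possibly on per-protocol membership. No alpha, power or sample-size figure changes, and the number of subjects affected cannot be estimated from the documents. The change is worth making before enrolment.

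**What to change.** 1. In exclusions 7 and 14, run the look-back window through admission and tick both criteria at Day -2 as well as at Screening.
2. Reconcile the exclusion 8 tick with section 7.4.4, Table 10 and section 9.2.1, so that the status of the Day -2 BMI is explicit.
3. Use one wording for the Day -2 check in the synopsis, sections 4.1 and 9.2.1, Appendix A footnote d and the criteria tables. If only some criteria are to be re-checked, list them.
4. Reconcile 28 days (section 9.1.1) with 27 days (section 9.2.1).
5. Carry the changes into the SAP copies: section 4.1 (Admission) and the criteria tables in sections 4.5.1 and 4.5.2.

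The cost is a wording amendment and two questions at the Day -2 visit; weight is already measured and BMI already calculated there. The downside is a few more late exclusions. Section 5.2 already replaces subjects lost before randomization, so the planned 72 is unaffected.
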